# Protocol Synopsis

Title	Investigator-initiated, Open Label Trial of Duobrii® for Plaque Type Psoriasis of the Hands and/or Feet
Sponsor	Ortho Dermatologics
Study Design & Overview	
This is an investigator-initiated, single-arm, open-label study, which will examine the effect of Duobrii® (halobetasol propionate 0.01%/tazarotene 0.045% lotion, HP/TAZ) on plaque type psoriasis of the hands and/or feet. Previous therapies used and failed will be captured for each subject. The findings in this study will result in at least one poster at a conference and at least one publication.

Primary Objective	Evaluate the percentage of patients achieving Palmoplantar Physician Global Assessment (ppPGA) of 0 (clear) or 1 (almost clear/minimal) after 24 weeks of treatment 
Secondary Objectives	
 
• Percentage of patients achieving ppPGA of 0 or 1 at weeks 8, 12 and 16
 
• Photography (hands and/or feet only) to assess treatment response at weeks 0, 2, 8, 12, 16 and 24
 
• Patient-reported outcomes to be evaluated by Dermatology Quality of Life Index (DLQI) at weeks 2, 8, 12, 16 and 24
 

	
 
• Treatment satisfaction to be evaluated by Numerical Rating Scale (NRS) at weeks 2, 8, 12, 16 and 24
 

Number of Subjects	22
Subject Selection Criteria	
Inclusion Criteria
 
 
1. Subject is able to provide written, informed consent and comply with the study protocol.
 
2. Subject is at least 18 years of age.
 
3. Subject has a diagnosis of plaque-type palmar and/or plantar psoriasis.
 
4. Patient has at least one psoriatic plaque outside of the palms and soles or psoriatic nail findings.
 
5. Subject has a ppPGA <math>\geq 3</math> at screening/baseline visit.
 
6. Subject is using adequate birth control during the study period as defined as follows: 
 
○ Option 1: Any one of the following highly effective methods: hormonal contraception (oral, injection, implant, transdermal patch, vaginal ring); intrauterine device (IUD); tubal ligation; or partner's vasectomy;
 
 
 
 
OR
 
 
○ Option 2: Male or female condom (latex condom or non-latex condom NOT
 

	
made out of natural [animal] membrane [for example, polyurethane]; PLUS one additional barrier method: (a) diaphragm with spermicide; (b) cervical cap with spermicide; or (c) contraceptive sponge with spermicide.
 
OR
 

1. Option 3: Abstinence from sex when it is a lifestyle choice, and not just a social circumstance.

 
Exclusion Criteria
 

1. Subject is not able to provide written, informed consent and comply with the study protocol.

2. Subject is less than 18 years of age.

3. Subject has non-plaque type psoriasis on the hands and/or feet.

4. Patient does not have any evidence of psoriasis elsewhere.

5. Subject has concurrent cutaneous disease affecting the hands and/or feet that would interfere with assessments.

6. Subject has a ppPGA < 3 at screening/baseline visit.

7. Subject refuses to discontinue concomitant prescription medications on hands and/or feet.

8. Subject has used prescription topical treatments or received phototherapy treatment for psoriasis within 2 weeks of screening/baseline visit.

--	--

	

9. Subject has used intralesional kenalog within 4 weeks of screening/baseline visit.

10. Subject has taken oral treatments for psoriasis within 4 weeks of screening/baseline visit.

11. Subject has received any treatment with biologic medications within 5 half-lives (if known) or 16 weeks prior to screening/baseline, whichever is longer.

12. Subject refuses to use adequate birth control during the duration of the study period.

13. Subject is currently pregnant or breastfeeding.

--	--

Study Treatment	Duobrii® (halobetasol propionate 0.01%/tazarotene 0.045% lotion), thin layer applied to affected areas of palms and/or soles once a day
Study Duration	The total duration of study activities is 24 weeks
Schedule of Efficacy and Safety Assessments	Screening/Baseline (Week 0), Week 2, Week 8, Week 12, Week 16, Week 24
Laboratory Work	None
Safety Evaluations	Safety and tolerability will be assessed by adverse events, physical examinations (including skin examinations and ppPGA scoring), and concomitant medication review
Statistical Analysis	Assuming the 40% of patients achieve ppPGA of 0 or 1 (similar to that seen with secukinumab) at week 24, this study requires 22 patients with a statistical power of 0.8 and 5% type one error
Budget Estimate	
\$120,845
 
88 tubes of Duobrii® (4 tubes of Duobrii® for each subject) supplied by Ortho Dermatologics.
 
The medication will be dispensed to the subject at week 0,2,8,16 and returned by the

	
subject at week 2,8,16,24.
 
Subjects will be compensated \$40 per study visit for their time and effort in participating in this study.

--	--

## Brief Summary of Research

The purpose of this research study is to examine the effect of Duobrii® (halobetasol propionate 0.01%/tazarotene 0.045% lotion, HP/TAZ) on plaque type psoriasis of the hands and/or feet. It is an investigator-initiated, single-arm, open-label study that will include 22 subjects. A thin layer of HP/TAZ will be applied to affected areas of palms and/or soles once a day. Treatment response will be clinically evaluated using the Palmoplantar Physician Global Assessment (ppPGA), which is a 5-point scale specifically applied to the hands and/or feet: 0 (clear), 1 (almost clear/minimal), 2 (mild), 3 (moderate), 4 (marked/moderate-to-severe), 5 (severe). The primary objective of the study is to evaluate the percentage of subjects achieving ppPGA of 0 or 1 after 24 weeks of treatment. Secondary objectives include evaluation of treatment response at earlier timepoints (Weeks 2, 8, 12, 16 and 24), including serial photography (also taken at week 0), patient-reported outcomes, and treatment satisfaction evaluation throughout the study period. In addition, safety and tolerability will be assessed by physical exam findings, adverse event monitoring, and concomitant medication review. Previous therapies used and failed will be captured for each subject.

## Background

Plaque type psoriasis of the hands and/or feet affects approximately 3-4% of patients with psoriasis. It is characterized by well-defined erythematous desquamative plaques located on the palms and soles, which may be limited to acral involvement or occur in combination with generalized psoriasis. Psoriasis that affects the hands and/or feet has a profound impact on quality of life (QoL) as it contributes to more physical disability and discomfort than patients with other forms of psoriasis, such as difficulty walking or using the hands.

Furthermore, psoriasis of the hands and/or feet is generally considered a therapeutic challenge because the thicker stratum corneum reduces the penetration of topical treatment agents. Systemic treatments (retinoids, psoralen–ultraviolet A [PUVA], methotrexate, cyclosporine, and biologic therapy) have shown limited efficacy on psoriasis in acral areas. Unfortunately, patients with hand and/or foot involvement often have too low of body surface area (BSA) to participate in clinical trials for new psoriasis

treatments, resulting in limited studies among this sub-population and no clear treatment algorithm.

The high unmet need for an effective treatment for psoriasis of the hands and/or feet has been addressed in recent years with the development of new medications for generalized psoriasis that may also be effective in treating disease localized to acral areas. In 2015, two multicenter, double-blind, randomized, parallel-group phase 3 studies were conducted to assess the safety, tolerability, and efficacy of lotion containing a combination of halobetasol propionate 0.01% and tazarotene 0.045% (HP/TAZ). The study population was subjects with moderate-to-severe psoriasis. The study results found that treatment success (defined as at least a 2-grade improvement from baseline Investigator Global Assessment score and a score of clear or almost clear) was achieved in around 40% of subjects by week 8, with substantial reductions in affected BSA, improvement in QoL, and a significant reduction in signs and symptoms of psoriasis.

These phase 3 studies did not include a sub-analysis of the effect of HP/TAZ on psoriasis of the hands and/or feet. Given that topical steroids and topical retinoids are separately recommended as treatment options for psoriasis of the hands and/or feet, an agent that safely combines these medications – and that has demonstrated safety and efficacy in generalized psoriasis – offers a potential treatment for psoriasis of the hands and/or feet.

The purpose of the study described in this protocol is to evaluate the effect of HP/TAZ on plaque type psoriasis of the hands and/or feet after 24 weeks of daily treatment. In addition, given the impact of this variant of psoriasis on QoL and the relative lack of currently available treatment options, this study will also evaluate the impact of HP/TAZ treatment on patient-reported QoL measures and treatment satisfaction scoring.

## Setting of Human Research

All research related activities will take place at Mount Sinai Downtown Department of Dermatology located at [name].

## Study Objectives

**Research Question:** What is the effect of Duobrii® (halobetasol propionate 0.01%/tazarotene 0.045% lotion, HP/TAZ) on plaque type psoriasis of the hands and/or feet?

This study will evaluate the hypothesis that HP/TAZ can improve plaque type psoriasis of the hands and/or feet. The purpose is to evaluate the effect of once daily treatment with HP/TAZ for 24 weeks among 22 subjects. Treatment response will be evaluated using the Palmoplantar Physician Global Assessment (ppPGA) 5-point scale. The primary objective is to determine what percentage of subjects achieve a ppPGA of 0 (clear) or 1 (almost clear/minimal) after 24 weeks of treatment.

## Study Design

The study aims to enroll 22 subjects at a single study site. This number assumes that 40% of subjects with plaque type psoriasis of the hands and/or feet will achieve a ppPGA of 0 or 1 (based on results seen with secukinumab) at week 24. Based on this, the study requires 22 patients to achieve a statistical power of 0.8 and 5% type one error. Based on retrospective data of similar studies conducted at this site, recruitment and enrollment of 22 subjects is feasible and expected to be completed in 12 months.

The study staff includes individuals who are experienced in conducting research and have comprehensive knowledge of the study population, culture, and society. This is a single-site study, so no management of information among sites will be necessary to protect subjects. This study is not classified as Community-Based Participatory Research.

Given that it is a single-arm, open-label study, there will be no randomization.

### Study Timeline:

- An individual subject will participate in study activities for a total of 24 weeks from initial screening/baseline visit at Week 0 to the final study visit at Week 24.
- It is anticipated that it will take up to 12 months to enroll all study subjects.

- It is estimated that this study will be completed, including completion of primary analyses, by the end of 2022.

Potential subjects will be screened for eligibility based on the inclusion and exclusion criteria indicated below.

*Inclusion Criteria*

1. Subject is able to provide written, informed consent and comply with the study protocol.
2. Subject is at least 18 years of age.
3. Subject has a diagnosis of plaque-type palmar and/or plantar psoriasis.
4. Patient has at least one psoriatic plaque outside of the palms and soles or psoriatic nail findings.
5. Subject has a ppPGA  $\geq 3$  at screening/baseline visit.
6. Subject is using adequate birth control during the study period as defined as follows:
  - a. Option 1: Any one of the following highly effective methods: hormonal contraception (oral, injection, implant, transdermal patch, vaginal ring); intrauterine device (IUD); tubal ligation; or partner's vasectomy;

OR

- b. Option 2: Male or female condom (latex condom or nonlatex condom NOT made out of natural [animal] membrane [for example, polyurethane]; PLUS one additional barrier method: (a) diaphragm with spermicide; (b) cervical cap with spermicide; or (c) contraceptive sponge with spermicide.

OR

- c. Option 3: Abstinence from sex when it is a lifestyle choice, and not just a social circumstance.

*Exclusion Criteria*

1. Subject is not able to provide written, informed consent and comply with the study protocol.
2. Subject is less than 18 years of age.
3. Subject has non-plaque type psoriasis on the hands and/or feet.
4. Patient does not have any evidence of psoriasis elsewhere.

5. Subject has concurrent cutaneous disease affecting the hands and/or feet that would interfere with assessments.
6. Subject has a ppPGA < 3 at screening/baseline visit.
7. Subject refuses to discontinue concomitant prescription medications on hands and/or feet.
8. Subject has used topical prescription treatments or received phototherapy treatment for psoriasis within 2 weeks of screening/baseline visit.
9. Subject has used intralesional kenalog within 4 weeks of screening/baseline visit.
10. Subject has taken oral treatments for psoriasis within 4 weeks of screening/baseline visit.
11. Subject has received any treatment with biologic medications within 5 half-lives (if known) or 16 weeks prior to screening/baseline, whichever is longer.
12. Subject refuses to use adequate birth control during the duration of the study period.
13. Subject is currently pregnant or breastfeeding.

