## Concomitant Therapies

All concomitant therapies must be recorded throughout the study period, from Screening/Baseline through Week 24. Subjects will be asked about concomitant therapies as part of the review of medical history at every study visit. With respect to specific classes of concomitant therapies:

- **Topical therapies:** Topical therapies that could affect the ppPGA evaluations (eg, corticosteroids, tar, anthralin, calcipotriene, tazarotene, methoxsalen, pimecrolimus, tacrolimus) are not permitted. The only allowable concomitant treatments throughout the study are non-medicated topical moisturizers. However, subjects should not use non-medicated topical moisturizers on the day of a study visit.
- **Phototherapy:** The use of phototherapy is not permitted at any time during the study.
- **Systemic therapy:** The use of systemic psoriasis medications is not permitted at any time during the study. These medications include those targeted for reducing TNF (including but not limited to infliximab or etanercept), drugs targeted for reducing IL-12, IL-17, or IL-23 (including but not limited to ustekinumab, tildrakizumab, secukinumab, ixekizumab, or brodalumab), alpha-4 integrin antagonists (including but not limited to natalizumab), systemic steroids, any conventional systemic therapy that could affect ppPGA evaluation (including but

not limited to methotrexate, cyclosporine, acitretin), and any other biological agent or other systemic medication that could affect the ppPGA evaluation.

- Other therapies: Every effort should be made to keep subjects on stable frequency and dosing of concomitant medications for general medical conditions. Such medications should be recorded at Week 0 (Screening/Baseline Visit) and if any changes to frequency or dosing are made during the duration of the study, such changes should be reported by the patient and recorded in the source documents.

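### Exclusion 10 sets its 4-week washout for oral psoriasis treatments only, so injected methotrexate and intramuscular or IV corticosteroid given for psoriasis have no washout

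*Combined protocol and SAP*

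**What the plan says.** Four exclusion criteria set a look-back period. They appear under Study Design (Study Timeline, Exclusion Criteria), and the synopsis has the same four:

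- Exclusion 8: "Subject has used topical prescription treatments or received phototherapy treatment for psoriasis within 2 weeks of screening/baseline visit".
- Exclusion 9: "Subject has used intralesional kenalog within 4 weeks of screening/baseline visit".
- Exclusion 10: "Subject has taken oral treatments for psoriasis within 4 weeks of screening/baseline visit".
- Exclusion 11: "Subject has received any treatment with biologic medications within 5 half-lives (if known) or 16 weeks prior to screening/baseline, whichever is longer".

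Once a subject is in the study, Concomitant Therapies applies a broader rule: "The use of systemic psoriasis medications is not permitted at any time during the study". Its list includes "alpha-4 integrin antagonists (including but not limited to natalizumab), systemic steroids, any conventional systemic therapy that could affect ppPGA evaluation", with examples that are "not limited to methotrexate, cyclosporine, acitretin), and any other biological agent or other systemic medication that could affect the ppPGA evaluation". No route of administration is specified there. For drugs taken for other diseases, the same section says "Every effort should be made to keep subjects on stable frequency and dosing of concomitant medications for general medical conditions".

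Screening and baseline are one visit. Study Procedures & Guidelines places the eligibility review, the medication review, the ppPGA, photography and the first dispensing of study drug all at Week 0.

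**The concern.** The on-study ban is defined by type of drug, while the washout is defined by route. Methotrexate therefore needs 28 days off if swallowed and none if injected. A corticosteroid needs 28 days off if injected into a lesion and none if given intramuscularly or intravenously for psoriasis. The protocol gives no reason for the difference, and its own wording treats these drugs as able to affect the ppPGA.

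The trial has a single arm. If some subjects still carry an effect of recent systemic treatment, no control group shows how much of an early score belongs to that treatment and how much to HP/TAZ. The data at risk are the Week 0 ppPGA, which must be 3 or more for entry, and the other assessments at Weeks 0 and 2.

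**Working it through.** **Step 1: does any criterion reach these treatments?**

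| Provision | Covers | Look-back | Injected methotrexate | IM or IV steroid for psoriasis |
|---|---|---|---|---|
| Exclusion 7 | Prescription medications on the hands or feet | None | No | No |
| Exclusion 8 | Prescription topicals, phototherapy | 2 weeks | No | No |
| Exclusion 9 | Intralesional kenalog | 4 weeks | No | No |
| Exclusion 10 | Oral psoriasis treatments | 4 weeks | No | No |
| Exclusion 11 | Biologics | 5 half-lives or 16 weeks, whichever is longer | No | No |
| Concomitant Therapies, systemic | Systemic psoriasis drugs, any route | None (on study only) | Barred from Week 0 | Barred from Week 0 |

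The remaining exclusions concern consent, age, type and extent of disease, severity, contraception and pregnancy. The last row is the only one that reaches these treatments. Study Timeline starts participation at the Week 0 screening/baseline visit, so the ban looks forward only. A subject dosed on day -1 who then stops complies with it.

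**Step 2: which assessments could be affected?**

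Inputs: last dose on day -1 (the latest day before Week 0), and a window of 4 × 7 = 28 days, taken from exclusions 9 and 10. Visit day = 7 × week number. The window closes on day -1 + 28 = 27.

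| Visit | Day | Days since dose (day + 1) | Position relative to day 27 |
|---|---|---|---|
| Week 0 | 0 | 1 | Inside |
| Week 2 | 14 | 15 | Inside, 27 - 14 = 13 days to spare |
| Week 8 | 56 | 57 | 56 - 27 = 29 days past |
| Week 12 | 84 | 85 | 84 - 27 = 57 days past |
| Week 16 | 112 | 113 | 112 - 27 = 85 days past |
| Week 24 | 168 | 169 | 168 - 27 = 141 days past |

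One of the 5 post-baseline visits lies inside the window. None of the 3 secondary response rates (Weeks 8, 12 and 16) does, and neither does the primary endpoint. The Week 2 DLQI asks about the preceding week, days 7 to 14, which is 7 + 1 = 8 to 14 + 1 = 15 days after the dose and wholly inside.

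**Step 3: how sensitive is this to the dosing day?**

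For a last dose on day d, the window closes on day d + 28. Week 2 is inside only if d + 28 ≥ 14, that is, d ≥ -14. With a last dose on day -15 the window closes on day 13, before the Week 2 visit. Day -1 is therefore the widest case. Conversely, for a day -1 dose to reach the first secondary response rate, its effect would have to last 57 days.

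**The case against.** The strongest reply is that the gap exists on paper but no consequence is shown. Nothing in the documents indicates that candidates at this site receive injected methotrexate or parenteral steroid for psoriasis. The Background section says systemic treatments have limited efficacy in acral areas, so any carry-over may be slight. The entry rule also helps: a subject whose disease is suppressed below ppPGA 3 by leftover drug is screened out, and one who still scores 3 or more would, if anything, tend to worsen as the drug wears off. The Week 0 review of previous therapies and concomitant medications would probably bring a recent dose to light. All of this stands as a limit on size. It does not close the gap, because recording a dose does not make a subject ineligible.

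A reader might infer more than the documents support in three ways:

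- **That the primary result is biased.** Week 24 is 141 days past the window even in the widest case. The endpoint is an absolute ppPGA of 0 or 1, so a distorted Week 0 score does not enter its calculation. It could act only through who is admitted.
- **That a withdrawal flare lifts milder patients over the entry threshold, and they then count as responders.** One such subject would be worth 1/22 = 4.5 percentage points. But the documents describe no flare and no timing for one, and a flare from stopping treatment does not fit a dose taken the day before. An earlier stop moves the window back and can take Week 2 out of it. This is an assumption.
- **That the DLQI loses its baseline.** The first DLQI is at Week 2, already 14 days into HP/TAZ, and no change-from-Week-2 analysis is planned. The missing Week 0 DLQI is a separate matter and adds no weight here.

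**Conclusion.** The point holds as a gap in one eligibility criterion. Required time off before Week 0 is 28 days for oral psoriasis treatment and 0 days for injected methotrexate or intramuscular or IV corticosteroid given for psoriasis, and this sits badly with the route-neutral ban that applies from Week 0.

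The consequence is small. Residual drug effect could touch the Week 0 ppPGA used for entry, the Week 0 photographs, and the Week 2 ppPGA, DLQI, satisfaction score and photographs. No listed response-rate endpoint falls inside the 28-day window. The direction of any effect cannot be settled from the documents, and the number of subjects affected is unknown and may be zero.

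This rests on two assumptions: a last dose on day -1, and the protocol's own 4 weeks as a reasonable length of carry-over. The documents give no duration for depot products, which might act for longer. Corticosteroids taken for another disease are outside the point, since the protocol asks for general medications to be kept stable. Changing the criterion is an optional improvement.

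**What to change.** Replace exclusion 10, in both the Protocol Synopsis and the main-text Exclusion Criteria, with:

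> Subject has received any non-biologic systemic drug treatment for psoriasis (including methotrexate and systemic corticosteroids), by any route, within 4 weeks of screening/baseline visit; phototherapy, including PUVA, is governed by exclusion 8.

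The closing clause is needed because the Background section counts PUVA among systemic treatments. Without it, the new text could be read as overriding the 2-week phototherapy washout. Exclusions 8, 9 and 11 stay as they are. Whether depot products need a longer interval is for the sponsor to decide.

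The cost is a wording change to one criterion in two places. A few candidates, possibly none, may be delayed by up to 4 weeks or not enrolled, so the target of 22 might be reached slightly later.
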